6.2. Statistical Considerations for Secondary Objectives

- 6.2.1. To examine the safety of axitinib, we will tabulate reported adverse events (adverse events will be recorded per CTCAE v4.0).
- 6.2.2. To examine the tolerability of axitinib, we will use the FKSI-15 (Functional Assessment of Cancer Therapy-Kidney Specific Index-15, Appendix E) questionnaire and compare changes in response between different time points.
- 6.2.3. We will evaluate disease-free survival by plotting Kaplan-Meier curves and estimating median recurrence-free survival. Time to death or recurrence will be defined as the time from treatment start until death, recurrence or progressive disease, whichever comes first. Patients who did not die, recur or have progressive disease will be censored at date of last follow-up. These will be compared to contemporary, matched (2:1 matching, for age group, stage and grade), historical controls. Although small differences in recurrence-free and overall survival might not be detected in this current trial, this information will help us when designing future large trials with this particular agent.

7. Treatment Plan (Table 4)

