Axitinib, a novel oral tyrosine kinase inhibitor of VEGFR-1, VEGFR-2, and VEGFR-3 has been recently investigated in 52 patients with metastatic ccRCC who failed prior systemic therapy with Interferon- α or Interleukin-2 ⁷. Responses were seen in 23 patients (44.2%), with two patients achieving complete response and one patient without prior nephrectomy having partial shrinkage of the primary renal tumor. Axitinib has also been investigated in 62 patients with metastatic ccRCC refractory to sorafenib ⁸, and partial response was observed in 22.6% of patients, with 80% experiencing some degree of tumor shrinkage. As such, axitinib appears to be a promising agent in the treatment of metastatic ccRCC.

We will be using the tyrosine kinase inhibitor axitinib up to 36 hours prior to radical nephrectomy in order to maximize the exposure time and potential benefit from this drug. This approach has been shown to be safe. Recently, Hellenthal et al ⁹ reported on a prospective trial of 3 months of the tyrosine kinase inhibitor sunitinib in 20 patients with renal cell carcinoma prior to radical nephrectomy. In 15 patients, sunitinib was stopped 1 day prior to surgery, and no surgical complications were attributable to sunitinib treatment. This is consistent with our experience ¹⁰, as we have not found a significant difference in surgical complications when comparing patients who received targeted therapy prior to radical nephrectomy with those who have not received any preoperative therapy.

Neoadjuvant therapy in the non-metastatic setting has the potential of improving overall survival, as seen from trials in non-metastatic bladder cancer ¹¹. To date, there are no published prospective trials of neoadjuvant targeted therapy prior to radical nephrectomy in patients without metastases. The use of axitinib in patients with ccRCC prior to radical nephrectomy has the potential of decreasing tumor size (which might allow us to perform a partial nephrectomy rather than a radical nephrectomy-thereby preserving renal function), regression of invasion into adjacent organs, regression of tumor venous thrombi, therefore improving surgical margins and treatment outcomes. In addition, collection of blood and tissue for molecular and genetic analysis is possible using this neoadjuvant approach, which will provide valuable information about molecular correlates of tumor response to

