4.2. Secondary Objectives

- 4.2.1. Study the safety, tolerability, and feasibility of Axitinib in patients with locally advanced biopsy-proven clear cell renal cell carcinoma prior to undergoing radical nephrectomy.
- 4.2.2. Assess disease-free survival and overall survival in patients with locally advanced biopsy proven clear cell renal cell carcinoma treated with 12 weeks of neoadjuvant Axitinib followed by radical nephrectomy.
- 4.2.3. Collect renal tissue, blood (serum, plasma, DNA, and PBMC), and urine for future correlative biomarker studies.

5. Assessment of Response

CT scans of the chest and abdomen will be evaluated by a urologist and an expert genitourinary radiologist. The urologist (investigator assessment) and the radiologist (independent assessment) will perform the tumor measurements. Response will be determined by the radiologist assessment. Tumor measurements will be documented in the tumor measurement form (one of the CRFs) and medical record. GURU will be used as electronic case report forms (CRF). RECIST version 1.0 criteria will be used as follows to quantify response to therapy:

- Complete Response (CR): Complete disappearance of renal mass.
- Partial Response (PR): At least a 30% decrease in the largest diameter (LD) of the renal mass taking as reference the baseline largest diameter.
- Progressive disease (PD): At least a 20% increase in the LD of the renal mass taking as reference the LD of the renal mass recorded since the treatment started. PD will also include development of any biopsy-proven metastatic disease.
- Stable Disease (SD): Neither sufficient shrinkage to qualify for PR nor sufficient increase to qualify for PD taking as reference the LD since the treatment started.
- Objective response rate (ORR) is defined as CR+PR.
- ORR will be evaluated when CT abdomen is done after 12 weeks of treatment (see Table 4).
- PD will be evaluated when CT abdomen is done after 7 weeks and 12 weeks of treatment (see Table 4).

6. Statistical Considerations

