7.2. Treatment Phase

7.2.1. Eligible patients will provide written informed consent.

7.2.2. Prior to the initiation of therapy, a surgical date will be established.

7.2.3. Treatment Assignment: Each patient will receive a total of 12 weeks of axitinib. Patients will take the last dose of axitinib 1.5 days prior to surgery.

7.2.4. Adverse events monitoring and reporting:

7.2.4.1. Adverse events:

7.2.4.1.1. The investigator is responsible for determining the attribution of adverse events to study drug.

7.2.4.1.2. Adverse events will be documented in the medical record and entered into the case report form according to the Recommended Adverse Event Recording Guidelines for Phase II protocol (see table below).

Recommended Adverse Event Recording Guidelines					
Attribution	Grade 1	Grade 2	Grade 3	Grade 4	Grade 5
Unrelated	Phase I	Phase I	Phase I Phase II	Phase I Phase II Phase III	Phase I Phase II Phase III
Unlikely	Phase I	Phase I	Phase I Phase II	Phase I Phase II Phase III	Phase I Phase II Phase III
Possible	Phase I Phase II	Phase I Phase II Phase III	Phase I Phase II Phase III	Phase I Phase II Phase III	Phase I Phase II Phase III
Probable	Phase I Phase II	Phase I Phase II Phase III	Phase I Phase II Phase III	Phase I Phase II Phase III	Phase I Phase II Phase III
Definitive	Phase I Phase II	Phase I Phase II Phase III	Phase I Phase II Phase III	Phase I Phase II Phase III	Phase I Phase II Phase III

7.2.4.1.3. Adverse events will be assessed at each patient visit, documented in the medical record, and entered into the CRFs. Adverse events should be treated appropriately. Such treatment may include changes in axitinib treatment including possible interruption or discontinuation, starting or stopping concomitant treatments, changes in the frequency or nature of assessments, hospitalization, or any other medically required intervention. Once an adverse event is detected, it should be followed until its resolution, and assessment should be made at

each visit of any changes in severity, the suspected relationship to the axitinib, the interventions required to treat it, and the outcome. In addition, Pfizer requires reporting of serious adverse events on the M.D. Anderson SAE forms. Reporting of adverse events will be done according to NCI Common Terminology Criteria for Adverse Events (CTCAE) version 4.0. The following items will be recorded at least:

- Event description
- Date of onset of AE
- CTCAE grade/severity (1,2,3,4,5)

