- 7.2.13. Surgery: Following successful completion of presurgical therapy, patients will undergo radical nephrectomy (open or laparoscopic at the surgeon's discretion), with retroperitoneal lymph node dissection. Extent of lymph node dissection will be recorded in the operative record and should include the ipsilateral nodes from renal hilum to aortic bifurcation, as well as the interaortocaval nodes from renal hilum to aortic bifurcation. Primary tumor specimens will be immediately sent to pathology on ice for further processing and correlative study specimen harvest. Routine perioperative parameters will be recorded and will include operative approach, operative time, estimated blood loss, ease of surgical dissection, comment on tissue planes, intraoperative complications (with grade), post-operative complications (with grade), blood transfusions, length of ICU stay (if applicable), length of hospital stay, perioperative mortality (within 30 days of surgery). The operating urologist will make a decision based on their extensive surgical expertise if these adverse events are attributable to axitinib or not. These events will certainly be monitored and recorded by the operating urologist, and discussed with the IND if they arise.

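### The planned adverse-event table can leave out Grade 1-2 surgical complications judged unrelated or unlikely to be related to axitinib

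*Combined protocol and SAP*

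**What the plan says.** Safety before nephrectomy is a secondary objective (4.2.1): "Study the safety, tolerability, and feasibility of Axitinib in patients with locally advanced biopsy-proven clear cell renal cell carcinoma". Section 6.2.1 gives its analysis in one sentence: "To examine the safety of axitinib, we will tabulate reported adverse events (adverse events will be recorded per CTCAE v4.0"). Section 6.2.2 covers tolerability by questionnaire. No other safety analysis is listed in 6.2.

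Three passages decide which events reach that table.

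- **7.2.4.1.2** says that events are "entered into the case report form according to the Recommended Adverse Event Recording Guidelines for Phase II protocol". In the grid, the Unrelated row begins "Unrelated Phase I Phase I Phase I Phase II", so Grades 1 and 2 carry Phase I only and Phase II first appears at Grade 3. The Unlikely row is the same.
- **7.2.4.1.3** sets no grade or attribution limit: "Adverse events will be assessed at each patient visit, documented in the medical record, and entered into the CRFs".
- **7.2.13** has graded intraoperative and post-operative complications recorded for patients who have surgery, along with blood loss, transfusions, operative time and length of stay. On attribution it says: "The operating urologist will make a decision based on their extensive surgical expertise if these adverse events are attributable to axitinib or not". The general rule in 7.2.4.1.1 is: "The investigator is responsible for determining the attribution of adverse events to study drug".

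**The concern.** Axitinib is taken until 1.5 days before radical nephrectomy, so surgical morbidity is a harm that this design in particular has to describe. The protocol treats it that way. Section 1 defends the short interval with surgical-complication evidence, including the centre's own experience that "we have not found a significant difference in surgical complications when comparing patients who received targeted therapy prior to radical nephrectomy" and patients who had no preoperative therapy. Section 6.1 makes reoperation for bleeding or dehiscence a ground for stopping recruitment.

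Without a concurrent control, a minor bleed or a slow wound in one patient cannot be reliably assigned to the drug or to the operation. If such an event is put down to surgery and the grid is followed, it leaves the safety table. The filter works in one direction only, because removing events can only lower the reported low-grade complication rate. At stake is whether a secondary safety objective is answered with all the complications the trial collects or with a subset selected by attribution.

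**Working it through.** The plan states no figure on this point, so there is none to reproduce. The check is a reading of the recording grid, a comparison of what is collected with what is analysed, and an illustration of scale.

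**1. The grid (7.2.4.1.2), Phase II entries**

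| Attribution | G1 | G2 | G3 | G4 | G5 |
|---|---|---|---|---|---|
| Unrelated | no | no | yes | yes | yes |
| Unlikely | no | no | yes | yes | yes |
| Possible | yes | yes | yes | yes | yes |
| Probable | yes | yes | yes | yes | yes |
| Definitive | yes | yes | yes | yes | yes |

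Cells: 5 × 5 = 25. Not recorded: 2 attributions × 2 grades = 4. Recorded: 25 − 4 = 21. A surgical complication is lost only if it is Grade 1-2 and is also rated Unrelated or Unlikely.

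**2. Other routes by which a surgical event is captured**

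- Reoperation for bleeding or for fascial dehiscence counts in the 6.1 stopping rule with no attribution test. Lesser bleeding or wound problems do not count there.
- Serious events go to the IND office regardless of attribution until 30 days after the last dose (7.2.4.2.2.3). With the last dose 1.5 days before surgery, that is 30 − 1.5 = 28.5 postoperative days. Non-serious events are outside this route.
- Table 4 marks adverse-event assessments at weeks 12 and 19 and none in the week 13 column, which holds the nephrectomy. The follow-up visits (7.3.1, 7.3.3) record morbidity that is treatment related, which again depends on attribution.
- Section 7.2.13 records graded complications with no attribution limit. The data would therefore exist, but 6.2 does not say that they will be tabulated.

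**3. Scale (assumed counts)**

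Assumptions: all 24 planned patients are operated on (n = 24), and 4 of them have one or more Grade 1-2 bleeding or wound complications and nothing more severe. Let d be the number of these patients whose complications are all rated Unrelated or Unlikely. The table then shows x = 4 − d. The exact (Clopper-Pearson) 95% limits are the 0.025 quantile of Beta(x, 24 − x + 1) and the 0.975 quantile of Beta(x + 1, 24 − x), with lower limit 0 when x = 0.

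| d dropped | Table shows | Rate | Exact 95% interval |
|---|---|---|---|
| 0 | 4/24 | 16.7% | 4.7 to 37.4% |
| 1 | 3/24 | 12.5% | 2.7 to 32.4% |
| 3 | 1/24 | 4.2% | 0.1 to 21.1% |
| 4 | 0/24 | 0% | 0 to 14.2% |

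For x = 0 the upper limit is 1 − 0.025^(1/24) = 0.142. The last row is the worst case. The documents give no low-grade complication rate and no expected split by attribution, so the table shows what is possible and does not predict it.

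**The case against.** The strongest reply is that the loss is not established. Section 7.2.13 is a separate instruction to record complications with grade. It calls them adverse events and sets no attribution limit, so the tabulation in 6.2.1 can be read to include them. Section 7.2.4.1.3 also enters events without limit. Attribution is in general the investigator's task, not the surgeon's alone. The consequential harms are covered through Grade 3-5 recording, serious-event reporting and the stopping rule. In a 24-patient single-arm trial, not naming every descriptive table does not rule one out.

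Much of this stands. The documents show a conflict between recording rules, not a certain omission, and the exposed events are the least severe ones. But nothing in the plan settles the conflict in favour of complete reporting, and 7.2.4.1.2 is the passage that explicitly sets the rule for a Phase II protocol.

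Two stronger readings are tempting, and the documents do not support them.

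- A reader might infer that perioperative complications, blood loss and transfusions will never be reported. The grid keeps 21 of 25 cells. Blood loss, operative time and stay are not graded events that the grid could remove. They, like transfusion, are simply not named in 6.2, which neither commits to reporting them nor excludes it. That is missing detail.
- A reader might infer that the gap bears on whether axitinib is judged to merit further study. Section 6.1 makes that decision on objective response alone: a posterior probability above 80% that the rate exceeds 20%, which it equates to 7 or more responders.

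**Conclusion.** The point holds in limited form. As written, the only planned safety analysis can leave out Grade 1-2 surgical complications judged unrelated or unlikely, and 7.2.4.1.2 and 7.2.4.1.3 disagree on whether such events are entered at all. Any resulting error understates low-grade surgical morbidity. Its size cannot be derived from the documents. Under the assumed 4 affected patients of 24, it runs from no understatement to 0% shown in place of 16.7%.

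The conclusion rests on the grid being followed as printed, on the operating urologist's judgement feeding the attribution used in the grid, and on the 6.2.1 table being built from what the grid admits. If the 7.2.13 record is the source instead, nothing is lost, but the plan does not say so. The change is worth making because it removes an attribution filter from a secondary safety objective at almost no cost.

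**What to change.** Add to 6.2.1 wording such as: *All intraoperative and post-operative complications recorded under 7.2.13 will be tabulated by type and grade regardless of attribution. The denominator is the number of patients operated on, and exact 95% intervals will be given. Attribution to axitinib will be shown separately.* Name the grading scale, since 7.2.13 does not.

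Reconcile 7.2.4.1.2 with 7.2.4.1.3, so that it is clear whether Grade 1-2 events rated Unrelated or Unlikely are entered in the case report form, and say whether complications recorded under 7.2.13 are subject to the grid.

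A short descriptive summary of blood loss, transfusion, operative time and length of stay would be a useful optional addition.

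The cost is a few sentences and one more table from data that 7.2.13 already collects. The small downside is that the reported complication rate will look less favourable, because events due to surgery alone are included. The sample size, stopping rules and success criterion do not change.

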6.1. Statistical Considerations for Primary Objective

The primary objective of this study is to assess objective response rate (ORR) following the administration of axitinib for 12 weeks in patients with locally advanced biopsy-proven clear cell renal cell carcinoma prior to undergoing radical nephrectomy.

Twenty-four patients will be treated in this study. We plan to abort recruitment should we have reason to believe that axitinib does not provide minimal efficacy, defined as $\Pr[\text{ORR} \geq 20\% \mid \text{data}] < 5\%$. We also plan to stop recruitment should we have reason to believe that it may be harmful, defined as $\Pr[\text{PD} > 20\% \mid \text{data}] > 80\%$, where PD is progressive disease. We will monitor study patients using the Bayesian approach of Thall¹². ORR will be evaluated at week 12 following initiation of treatment and PD will be evaluated at week 7 and week 12 following initiation of treatment.

For calculating our stopping criteria and operating characteristics for futility and disease progression, we assume that $\text{ORR} \sim \text{Beta}(0.4, 1.6)$ and $\text{PD} \sim \text{Beta}(0.4, 1.6)$. The prior for both ORR and PD has a mean of 20% and a standard deviation of 23%.

We will continually evaluate patients for excessive PD as they are being enrolled. We will begin evaluating for minimal ORR after the first 18 patients have been treated and evaluated for responses. Given that those patients who have PD will be immediately terminated from the study treatment to have a nephrectomy, we do not feel that delaying evaluation for futility until 18 patients are treated will jeopardize patient wellbeing. Once the minimum number of patients has been treated and assessed for ORR and PD, we will continue to assess both outcomes after each additional patient has been evaluated.

The trial will be stopped for futility (low ORR) if

$$[\# \text{ of patients with ORR} / \# \text{ of patients evaluated at Week 12}] \leq 1/18.$$

Likewise, the trial will be stopped for excessive PD if

$$[\# \text{ of patients with PD} / \# \text{ of patients evaluated at Week 7 and 12}] \geq 3/6, 4/9, 5/13, 6/17, 7/21.$$

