7.2.8. Treatment intake monitoring

7.2.8.1. The patient will be provided with a pill diary to record date of treatment, day of treatment, time of treatment, dose. Missed doses will be recorded as well. (Appendix J)

7.2.8.2. Pill counting. The patient will bring the axitinib bottle(s) when coming for a clinical visit. Pills will be counted by nurse/provider and recorded on a CRF and medical records.

7.2.8.3. Unused or expired axitinib pills will be disposed per MDACC institutional policy.

7.2.9. Treatment Start-Eligible patients will start treatment within 4 weeks of enrollment.

7.2.10. A history, physical examination, medication list (Appendix J), ECOG Performance Status, Adverse Events, FKSI-15 questionnaire (Appendix E) will be performed and recorded in the medical record and appropriate CRFs on weeks 3, 7, and 12. An EKG will be performed and the results recorded in the medical record and appropriate CRFs on weeks 3 and 12.

- 7.2.11. Laboratory studies that include CBC, CMP, PT, PTT, UA will be obtained prior to starting axitinib, then at week 3, week 7, and week 12 after starting axitinib. In addition, blood studies for TSH, free T3, and free T4 will be performed prior to starting axitinib, and then blood studies for TSH will be performed at week 3, week 7, and week 12 after starting axitinib. With each blood draw, 4 tubes of research blood will be drawn and processed for DNA, serum, plasma, and PBMC isolation for correlative studies, after the patient has provided informed consent.
- 7.2.12. Imaging: CT scans of the chest and abdomen (renal protocol) will be obtained on week 7 and week 12 of therapy. Patients with evidence of disease progression by RECIST version 1.0 at week 7 (primary or metastatic) will be considered treatment failures and their axitinib treatment will be permanently discontinued. Subsequently, their surgery will be performed earlier than initially planned. The urologist (investigator assessment) and the radiologist (independent assessment) will perform the tumor measurements. Response will be determined by the radiologist assessment. Tumor measurements will be documented in the tumor measurement form (one of the CRFs) and medical record.

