7.3. Post-treatment follow-up

- 7.3.1. Patients will be seen at week 19 (+/- 1 week) and evaluated with CT chest and abdomen (renal protocol), full laboratory analysis (CBC, CMP), collection of blood and urine for research, and full history and physical examination. Evidence of disease recurrence [If a patient develops any evidence of biopsy-proven RCC after axitinib/surgery (in the form of local disease or distant disease), the patient will be labeled as having disease recurrence] or treatment related morbidity will be recorded. Pathology will be reviewed and will be assessed for histology, Fuhrman grade, percentage tumor viability, pathologic tumor size, presence of venous, extracapsular, sinus, or nodal involvement.
- 7.3.2. A history, physical examination, medication list (Appendix J), ECOG Performance Status, Adverse Events, FKSI-15 questionnaire (Appendix E) will be performed and recorded in the medical record and appropriate CRFs on week 19.
- 7.3.3. Patients will be followed with similar evaluations every 4 months (+/- 2 weeks) for the first year, then every 6 months (+/- 2 weeks) for the next 2 years, , then yearly (+/- 1 month) until year 5 postoperatively. Evidence of recurrence or treatment related morbidity will be recorded.

8. Tissue, Blood, and Urine Banking

- 8.1. Tissue-Kidney biopsy specimen and kidney surgical specimen will be collected
 - 8.1.1. Kidney biopsy specimen. A total of 4 adequate biopsy cores are needed. Each core should undergo touch prep by cytopathologist to ensure biopsy quality (ie, malignant cell present with minimal necrosis/hemorrhage). More cores will be obtained if touch prep shows inadequate diagnosis (to obtain a total of 4 adequate cores).
 - 8.1.1.1. One core will be fixed for pathologic evaluation and sent for pathology department for review prior to starting treatment.
 - 8.1.1.2. Three cores will be immediately placed in 3 separate cryotubes, labeled appropriately, and stored at -70° to -80°C for future use.
 - 8.1.1.3. All 4 touch prep slides will be labeled appropriately, and stored at room temperature for future use.
 - 8.1.2. Kidney surgical specimen:
 - 8.1.2.1. Tissues from final kidney surgical specimen (4 pieces of tumor, 5-10mm diameter each; and 4 pieces of normal appearing kidney cortex, 5-10mm diameter each) will

be collected in the pathology department. Each piece will be placed in a separate cryotube, labeled appropriately, and stored at -70° to -80°C for future use.

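### Section 6.2.3 counts growth of a primary tumour that is then resected as a recurrence-free survival event, which upfront-nephrectomy controls could not have

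*Combined protocol and SAP*

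**What the plan says.** Section 6.2.3 promises Kaplan-Meier curves for disease-free survival and an estimate of median recurrence-free survival, using the two names for one quantity. The event is defined thus: "Time to death or recurrence will be defined as the time from treatment start until death, recurrence or progressive disease, whichever comes first". On the comparison it says: "These will be compared to contemporary, matched (2:1 matching, for age group, stage and grade), historical controls". It does not give the controls' treatment, their time origin or the events to be counted for them. It adds that small differences may go undetected and that the information will help in designing later large trials.

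Section 5 holds the only definition of progressive disease (PD). It has two parts: "At least a 20% increase in the LD of the renal mass", and biopsy-proven metastasis. PD is read on CT at weeks 7 and 12; Table 4 places nephrectomy at week 13. Section 7.2.12 says that patients with "disease progression by RECIST version 1.0 at week 7 (primary or metastatic) will be considered treatment failures", so growth of the primary alone is enough. It continues: "Subsequently, their surgery will be performed earlier than initially planned". Section 6.1 likewise says that "those patients who have PD will be immediately terminated from the study treatment to have a nephrectomy". Section 7.3.1 defines recurrence separately, as biopsy-proven renal cell carcinoma, local or distant, found after axitinib or surgery.

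**The concern.** Read together, these sections make a patient whose tumour grew by 20%, was resected and never came back a permanent recurrence-free survival failure at week 7 or 12. As a description of one arm that is a legitimate event-free survival endpoint. In a comparison with patients operated on at once it is not, because they have no tumour left in place under repeat CT. Applying the identical definition to both groups does not help: one group cannot have the event.

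At stake is the planning value of the comparison. A gap produced by the event definition could be read as a difference in outcome and carried into the design of a later trial. Only the primary-growth part of PD causes this; metastasis is a proper event in either group. Overall survival, the response-rate analysis and the stopping rules are untouched.

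**Working it through.** **1. The plan's own figures.** Section 6.2.3 gives no rate, power or event count. The nearest figures that depend on PD frequency are in Table 2. The Section 6.1 boundaries, "3/6, 4/9, 5/13, 6/17, 7/21", were carried forward (3 from patient 6, 4 from patient 9, and so on) with a look after each of patients 6 to 23, using exact binomial recursion. Early-stopping probabilities, computed against stated, at true PD rates of 0.10 to 0.30: 0.054 v 0.056, 0.169 v 0.165, 0.344 v 0.346, 0.544 v 0.537, 0.723 v 0.724. Table 2 reproduces.

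With the Beta(0.4, 1.6) prior, r PDs in 24 give a Beta(0.4 + r, 1.6 + 24 − r) posterior. Pr(PD > 20%) is 0.688 at r = 6 and 0.831 at r = 7, against the 0.80 limit. So the rule allows 24 patients with six PDs of any type, and seven if the 24th patient is the seventh.

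**2. Assumptions for size.** The documents give no rate of primary-growth PD and no control survival. I assume no drug effect, a constant hazard, control median M of 24, 48, 72 or 120 months, 24 trial patients and 48 controls (2:1 read as two controls per patient), and no censoring at 36 months.

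**3. Formulas.**
- Control: S(t) = exp(−ln2 · t/M).
- Trial, with a proportion p having primary-growth PD unrelated to later risk: (1 − p)·S(t). The loss at 36 months is p·S(36). This is an upper value.
- If such patients have three times the later hazard: control = (1 − p)e^(−λt) + p·e^(−3λt), with λ set so that the control median is M; trial = (1 − p)e^(−λt); loss = p·e^(−3λ·36).
- 95% half-width of the difference: 1.96·√[S(1 − S)(1/24 + 1/48)].
- Largest opposing time shift, with controls timed from surgery and trial patients having no hazard for 13 weeks (2.99 months): S(33.01) − S(36). Net with one such patient: (23/24)·S(33.01) − S(36).

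| 36-month result (points unless stated) | M = 24 | M = 48 | M = 72 | M = 120 |
|---|---|---|---|---|
| S(36), proportion | 0.354 | 0.595 | 0.707 | 0.812 |
| Loss, 1 patient, upper value | 1.5 | 2.5 | 2.9 | 3.4 |
| Loss, 1 patient, triple later hazard | 0.2 | 0.9 | 1.5 | 2.3 |
| Loss, 5 patients, upper value | 7.4 | 12.4 | 14.7 | 16.9 |
| Loss, 6 patients, upper value | 8.8 | 14.9 | 17.7 | 20.3 |
| 95% half-width | 23.4 | 24.1 | 22.3 | 19.1 |
| Largest opposing time shift | +3.2 | +2.6 | +2.1 | +1.4 |
| Net, 1 patient with that shift | +1.6 | 0.0 | −1.0 | −2.0 |

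Up to five such patients, the loss stays inside the half-width at every M. At six it exceeds it only at M = 120 (20.3 v 19.1). If the hazard is equal from day 1 the time shift is nil.

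**4. The median, which the plan names.** Solving (23/24)·S(t) = 0.5, one such patient moves a 24-month median to 22.5 months and a 48-month median to 45.1. Section 7.3.3 ends trial follow-up at year 5, so longer medians may not be reached; that is why 36-month survival is used above.

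**5. Cross-check by simulation.** Separate assumptions: equal true hazards, control 5-year recurrence-free survival of 0.5 to 0.8, PD at week 7 or 12 with equal chance, 1,500 runs per setting. The median apparent hazard ratio, trial v control, was 0.96–1.00 with no such patient, 1.19–1.48 with two and 1.40–2.04 with four. A two-sided 5% log-rank test, which the plan does not specify, rejected in 4–6%, 8–10% and 14–28% of runs. An effect within sampling error in one trial is still a shift in the estimate.

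**The case against.** **The controls' treatment is not written.** This stands in full. Section 1 mentions an earlier comparison with patients given no preoperative therapy, but that concerned surgical complications and was a different exercise. Upfront nephrectomy is a reasonable expectation, not a documented fact, and the conclusion stays conditional on it.

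**Progressive disease in 6.2.3 may mean post-operative progression.** Section 6.2.3 does not refer back to Section 5, and the follow-up paragraphs in 7.2.6 speak of disease progression after treatment has stopped. This is possible but less natural: post-operative disease is already covered by recurrence, listed separately in the same sentence, and no other definition of PD exists.

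**PD is a standard component of event-free survival.** Agreed. The point concerns only the control comparison and the disease-free and recurrence-free labels.

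**The comparison is secondary, without power, test or decision rule, and the plan warns of its limits.** Agreed; this keeps the point minor.

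**Matching.** A reader might infer that the plan matches on post-axitinib stage and grade. Section 6.2.3 does not say which stage or grade is meant, so this needs clarifying and is not shown to be an error.

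**Conclusion.** The point holds in conditional form. A stated rule, not merely a missing detail, puts into the control comparison an event that upfront-nephrectomy controls could not have. Its size is at most 1.5 to 3.4 points of 36-month recurrence-free survival per affected patient, or 0.2 to 2.3 if such growth marks a tripled later hazard, and nil if nobody has it. These figures rest on assumed control medians, a constant hazard and no drug effect.

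Two stronger readings are tempting and are not supported. The first is that the comparison is biased against axitinib overall. The event alone works that way, but the controls' time origin is unstated, and timing them from surgery could offset it; with one such patient the net runs from −2.0 to +1.6 points. The second is that the stopping rule implies a bias of 9 to 20 points. That needs six PDs, all of them primary growth and all unrelated to later risk. Nor is six a strict ceiling, since seven is possible. The documents support neither that frequency nor that composition.

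**What to change.** For the control comparison only:

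1. Count death, biopsy-proven recurrence or metastasis, and failure to reach nephrectomy because of disease, with a stated event date for the last. Do not count growth of a primary that is then resected. Report pre-surgical PD separately.
2. State the controls' treatment and time origin. Show results both from nephrectomy and from the start of each group's treatment strategy (axitinib start; surgery for upfront-nephrectomy controls). Name the limit of each: the first omits patients who never reach surgery; the second can favour the trial arm by the pre-surgical interval, up to 1.4 to 3.2 points here.

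Keep the treatment-start curve that includes PD as the single-arm description, labelled event-free survival. Say whether the matching stage and grade are pre-treatment. Matching on biopsy grade should not be required: the documents list Fuhrman grade only for the pathology reviewed at the week-19 visit (7.3.1).

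The cost is wording in 6.2.3 and, for controls, treatment and dates from their charts. No visit, sample size, primary analysis or stopping rule changes. Three limits remain. The compared endpoint is narrower than the single-arm one. Controls found through nephrectomy records will all have reached surgery, so failure to reach it can then arise only in trial patients; the nephrectomy-origin result shows the comparison without it. The week-7 and week-12 CTs may also find metastases sooner than in controls.
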